20.0 Withdrawal of Subjects

N/A: This study is not enrolling subjects. This section does not apply.

*20.1 Describe **anticipated** circumstances under which subjects may be withdrawn from the research without their consent.*

Response:

If the first venipuncture procedure is failed, subject will be withdrawn from the study.

20.2 Describe any procedures for orderly termination.

NOTE: Examples may include return of study drug, exit interview with clinician. Include whether additional follow up is recommended for safety reasons for physical or emotional health.

Response:

If a subject is withdrawn from the study, we will not collect any data from the subject.

20.3 Describe procedures that will be followed when subjects withdraw from the research, including retention of already collected data, and partial withdrawal from procedures with continued data collection, as applicable.

Response:

If a subject withdraws from the research in the ED, no study data will be collected for the study. The signed consent/assent document will be kept in the file cabinet in the research office, Conventus building, Room 5201.

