6.0 Inclusion and Exclusion Criteria

*6.1 Describe the criteria that define who will be **included** in your final study sample.*

NOTE: This may be done in bullet point fashion.

Response:

Inclusion criteria:

1. Male or female patients 6 to 18 years old

2. Need venipuncture procedure including IV's line placement and/or phlebotomy at the ED.

6.2 Describe the criteria that define who will be *excluded* from your final study sample.

NOTE: This may be done in bullet point fashion.

Response:

Exclusion criteria include:

1. Patients is sensitive to cold i.e. Raynaud's disease.
2. Sickle cell disease, diabetic
3. Critically ill patients
4. Mentally challenged patients
- 5.. GCS< 15
- 6.. Patient with altered sensation
- 7.. Patients needing more than one attempt for IV placement or phlebotomy

6.3 Indicate specifically whether you will include any of the following special populations in your study using the checkboxes below.

NOTE: Members of special populations may not be targeted for enrollment in your study unless you indicate this in your inclusion criteria.

Response:

- Adults unable to consent
- Individuals who are not yet adults (infants, children, teenagers)
- Pregnant women
- Prisoners

6.4 Indicate whether you will include non-English speaking individuals in your study. Provide justification if you will exclude non-English speaking individuals.

*In order to meet one of the primary ethical principles of equitable selection of subjects, non-English speaking individuals may **not** be routinely excluded from research as a matter of convenience.*

In cases where the research is of therapeutic intent or is designed to investigate areas that would necessarily require certain populations who may not speak English, the researcher is required to make efforts to recruit and include non-English speaking individuals. However, there are studies in which it would be reasonable to limit subjects to those who speak English. Some examples include pilot studies, small unfunded studies with validated instruments not available in other languages, studies with numerous questionnaires, and some non-therapeutic studies which offer no direct benefit.

Response:

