10.0 Procedures Involved

10.1 Provide a description of all research procedures or activities being performed and when they are performed once a subject is screened and determined to be eligible. Provide as much detail as possible.

NOTE: This should serve as a blueprint for your study and include enough detail so that another investigator could pick up your protocol and replicate the research. For studies that have multiple or complex visits or procedures, consider the addition of a schedule of events table in in your response.

Response:

Randomization of subject into one of the three study arms

There will be three arms of this study with each arm testing a different pain reducer: Buzzy Bee, Vapocoolant, and placebo. We will use a sham device e.g. a band around the arm for placebo control.

After obtaining informed consent, the patients will be randomized into one of the three groups following a randomization table created by a statistician. Whichever intervention is randomly selected will be performed on patient prior to the needle stick.

These methods have been used in the ED as part of routine procedures to help patient for pain relief from a needle stick, the RNs are familiar with these methods. However, for the purpose of this study, the training videos will be uploaded in the Kaleidoscope Talent management for RNs to review the procedure and help them to refresh their memories.

Videotaping of subject

Using a camera, an ED research assistant will videotape subject's whole body including the facial expression while phlebotomy and IV catheter placement is performed for scoring of the PBCL. We will tape the entire venipuncture procedure starting from sterilization and ending at the time when the venipuncture is completed. If the first venipuncture procedure attempt is failed, we will not tape the second attempt. This subject will be withdrawn from the study.

Obtaining pain scores from subject and legal guardian using the Faces Pain Scale-Revised instrument

Before and after the venipuncture procedure, we will ask the legal guardian and subject to complete a Faces pain scale revised form. Since the revised form is validated to use for both adult and children, the same document will be used for the legal guardian and children for this study. This document is attached with this submission.

Reviewing of the videotape

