17.0 Data Management and Analysis

17.1 *Describe the data analysis plan, including any statistical procedures. This section applies to both quantitative and qualitative analysis.*

Response:

All data analyses will be performed with SAS (version 9.2; SAS Institute, Inc., Cary, NC) and R (version 3.0.3) software. Chi-square and Fisher's exact test will be used to compare adverse events (e.g., systemic reaction, anaphylaxis, SOB, dyspnea, excess bleeding or hematoma formation), venipuncture and catheterization first attempt success, and number of patients with no to mild pain during needle insertion.

The Kruskal-Wallis test will be used to compare each of the two observers' assigned scores on the PBCL across three time periods: pre, procedure and post-procedure. Pre-procedure is defined as the time period prior to needle insertion including the placement of Vapocoolant, pain control or sham device up to needle insertion. The procedure period is defined as needle insertion through withdrawal. Post-procedure is defined as the 2 minute time period after needle withdrawal. Only patient and observer pain scores will be used for first-time needle insertion. If first attempt is failed, subject will be withdrawn from the study. Comparisons of pain scores of the five intervention groups to placebo (sham device) will be analyzed via ANOVA.

17.2 If applicable, provide a power analysis.

NOTE: This may not apply to certain types of studies, including chart/records reviews, survey studies, or observational studies. This question is asked to elicit whether the investigator has an adequate sample size to achieve the study objectives and justify a conclusion.

Response:

For chi-square analysis, based on a medium effect size of 0.3, alpha of 0.05, degree of freedom of 8, and 80% power it is estimated we will need a total of 168 subjects (56 per group). (*QFAB Bioinformatics*. 2015)

17.3 Describe any procedures that will be used for quality control of collected data.

Response:

Our RA will double check the data form to assure accuracy and completeness of data collection, if there is any missed data point, the RA will fill in the missing information immediately.

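### Withdrawing children after a failed first stick empties the planned first-attempt-success comparison and limits the pain comparison to a set formed after randomisation and treatment

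*Combined protocol and SAP*

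**What the plan says.** **Order of events.** Section 10.1 randomises after consent and then states: "Whichever intervention is randomly selected will be performed on patient prior to the needle stick". Failure of the stick therefore comes after both randomisation and treatment.

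**What follows a failure.** Section 20.1: "If the first venipuncture procedure is failed, subject will be withdrawn from the study". The same rule appears in 10.1, in 17.1, and in the Data Management and Analysis text repeated at the end of the document. Section 20.2: "If a subject is withdrawn from the study, we will not collect any data from the subject". Section 6.2, where the form asks who is excluded "from your final study sample", lists as item 7 "Patients needing more than one attempt for IV placement or phlebotomy".

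**What is to be analysed.** Section 17.1 assigns chi-square and Fisher's exact tests to adverse events and to "venipuncture and catheterization first attempt success, and number of patients with no to mild pain during needle insertion". It also restricts pain scores to the first insertion. Section 2.1 makes reduction of pain and anxiety the primary outcome.

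**What is taped.** Section 10.1: "We will tape the entire venipuncture procedure starting from sterilization and ending at the time when the venipuncture is completed". It continues: "If the first venipuncture procedure attempt is failed, we will not tape the second attempt".

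The documents give no first-stick failure rate, do not say whether withdrawn children are replaced, and define no all-randomised analysis set.

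**The concern.** The plan names first-attempt success as something to compare and, in the same section, removes every child who lacks it. One of the two has to give way.

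The same rule selects the children in whom pain is compared. Success at the first stick is an event after treatment, so the groups being compared are no longer simply those formed by randomisation. No check is planned that this selection is balanced across arms. Events such as excess bleeding or haematoma in a failed stick also drop out of the adverse-event comparison. If first-attempt data are not recorded at the bedside, they may not be recoverable later.

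**Working it through.** **1. The plan's sample size reproduces.** Inputs from 17.2: effect size w = 0.3, alpha 0.05, 8 degrees of freedom, 80% power. The noncentral chi-square needs a noncentrality of 15.022, and N = 15.022 / 0.3² = 166.9. That is 167, or 168 in three equal arms of 56. Power at 168 is 80.3%. The enrolment target in 5.1 is the same 168, so nothing is added for failed sticks.

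**2. First-attempt success under the written rule.** With failures removed, the table is successes (n₁, n₂, n₃) and failures (0, 0, 0). The expected failure count in each arm is nᵢ × 0 / N = 0, so the chi-square statistic is undefined. With illustrative counts 50/0, 45/0 and 48/0 the software stops on zero expected counts. For Fisher's test only one table is possible given the margins; 50/0 versus 45/0 gives p = 1. The true success rates make no difference to this.

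**3. Numbers affected.** The failure rate f is an assumption.

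| f | Leave the analysis, 168f (per arm) | Analysed | Power, plan's 8 df | Randomised if replaced to 168, 168/(1−f) |
|---|---|---|---|---|
| 10% | 17 (5.6) | 151 | 75.0% | 187 |
| 20% | 34 (11.2) | 134 | 68.7% | 210 |
| 30% | 50 (16.8) | 118 | 62.0% | 240 |

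The middle columns apply if 168 counts everyone randomised and failures are not replaced. Replacement restores the numbers but leaves the failure row empty and the selection in place. The power loss depends on the plan's 8 degrees of freedom; steps 2 and 4 do not.

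**4. Possible bias in the pain comparison.** Assume no treatment effect on pain, and that pain and a latent tendency to fail are bivariate normal with correlation r, the same in each arm. Let z = Φ⁻¹(1−f) and m = φ(z)/(1−f). Mean pain among successes is −r·m, in SD units.

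- m = 0.195 at f = 10%, 0.350 at 20%, 0.497 at 30%.
- Equal f in both arms, or r = 0: difference 0.
- 10% versus 20%, r = 0.3: 0.3 × (0.350 − 0.195) = 0.046 SD.
- 10% versus 30%, r = 0.5: 0.5 × (0.497 − 0.195) = 0.151 SD.

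With r positive, the arm with more failures looks less painful.

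The variance of pain among successes is 1 − r²·m·(z + m). In the last case this is 0.928 (10% arm) and 0.873 (30% arm). Without replacement, 50.4 versus 39.2 children are analysed, SE = √(0.928/50.4 + 0.873/39.2) = 0.202, and the two-sided type I error of a two-arm test is 11.6%. With replacement to 56 versus 56, SE = 0.179 and it is 13.4%. In the milder case it is 5.6% or 5.7%.

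**The case against.** **Section 20.2 may mean no further data.** It answers a question about orderly termination, and the first attempt is already on tape when failure becomes known. Section 17.1's restriction to the first insertion could likewise be read as keeping first-attempt scores. This stands to the extent that first-attempt data may exist. It does not rescue the comparison: the next sentence of 17.1 withdraws the child, item 7 of 6.2 excludes the child, and no use of such data is planned. The phrase about the final study sample is the form's printed question, but the investigators entered item 7 in answer to it.

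**Failures could be counted another way.** Needing a second attempt is itself a record of failure, and counts by arm might be rebuilt from the randomisation table, withdrawal status and the electronic chart (10.4). That is possible, but the plan does not provide for it, and the enrolment log fields listed in 18.1 A include no arm, outcome or reason for withdrawal.

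**Adverse events.** A reader might infer that the adverse-event comparison is also impossible, or that adverse events are not recorded at all because Section 19 answers its safety questions as not applicable. Neither follows. The comparison can be run in the retained children, Section 19 concerns safety monitoring, and the data collection form is not shown. What is lost is events in failed sticks.

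**No bias is shown.** This is correct. The failure rates, their difference by arm and the correlation are all assumed. The milder case is negligible. The 12–13% is for a two-arm test; under the planned three-group ANOVA the same extreme assumptions give about 9–13%, depending on the third arm.

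**One completed stick is a cleaner setting for pain.** Restricting to it avoids contamination by a repeat attempt. Rating pain straight after the first attempt, and scoring only the first-attempt video, serves the same purpose without discarding the child.

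**Conclusion.** The contradiction is certain from the text. With failed first sticks withdrawn and excluded, the named comparison of first-attempt success cannot show a difference. Reading 20.2 as no further data does not change this. The adverse-event comparison is incomplete rather than impossible.

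The primary pain comparison applies only to first-stick successes, a set formed after randomisation and treatment. A reader might infer that the pain result is therefore biased. The documents do not support that: bias requires failure, or its relation to pain, to differ by arm, and they give no figure on either. The range of 0 to 0.15 SD above illustrates assumptions and does not estimate what will happen in this trial.

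First-attempt success is not the primary outcome. The case for change rests on the contradiction and on leaving randomised, treated children out of the pain analysis, and it holds whatever the size of any bias.

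**What to change.** Reconcile 6.2 item 7, 10.1, 17.1, 20.1, 20.2 and the repeated analysis text at the end of the document, so that a failed first attempt does not remove a randomised child from data collection or analysis. Specifically:

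- Record assigned arm, first-attempt success (yes/no) and adverse events for every randomised child, and align the Section 19 answers with the planned adverse-event comparison.
- Keep the pre-procedure Faces Pain Scale–Revised and the first-attempt video. Take the child and guardian ratings after the first attempt whatever its result. Score the pre-procedure and procedure periods of the PBCL from that video.
- Analyse all randomised children by assigned arm, except families who themselves withdraw, with those counts reported by arm. Use first-stick successes as a sensitivity analysis.
- State in 5.1 whether 168 counts all randomised children.

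Management of a second attempt is unchanged.

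**Cost.** Wording in eight places (the six above, Section 19, which holds several answers, and 5.1), up to three form fields if the form lacks them, and one brief rating between attempts. That rating may partly reflect anticipation of another stick. The post-procedure PBCL window may be cut short in these children and should be flagged. Separately, the two-minute post-procedure period in 17.1 does not fit the end of taping in 10.1; that needs its own reconciliation.

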21.0 Risks to Subjects

21.1 List the reasonably foreseeable risks, discomforts, hazards, or inconveniences to the subjects related to their participation in the research. Consider physical, psychological, social, legal, and economic risks. Include a description of the probability, magnitude, duration, and reversibility of the risks.

NOTE: Breach of confidentiality is always a risk for identifiable subject data.

Response:

Some subjects may find the device a discomfort, however previous studies on devices show minimal risk for discomfort or hazards. In addition, breach of confidentiality is the potential risk for this study.

21.2 Describe procedures performed to lessen the probability or magnitude of risks, including procedures being performed to monitor subjects for safety.

Response:

Nurse will follow instruction when place the device on subject to avoid any unnecessary discomfort. In addition, please refer to section 18 A for answers on protecting data confidentiality.

21.3 If applicable, indicate which procedures may have risks to the subjects that are currently unforeseeable.

Response:

None

21.4 If applicable, indicate which research procedures may have risks to an embryo or fetus should the subject be or become pregnant.

Response:

The devices have no known risk to embryo or fetus.

21.5 If applicable, describe risks to others who are not subjects.

Response:

None

22.0 Potential Benefits to Subjects

22.1 Describe the potential benefits that individual subjects may experience by taking part in the research. Include the probability, magnitude, and duration of the potential benefits. Indicate if there is no direct benefit.

NOTE: Compensation **cannot** be stated as a benefit.

Response:

A subject may experience less pain/ anxiety if he/she is provided with the device or the vapocoolant while the venipuncture procedure is performed.

23.0 Compensation for Research-Related Injury

- N/A: The research procedures for this study do not present risk of research related injury (e.g. survey studies, records review studies). This section does not apply.

23.1 **If the research procedures carry a risk of research related injury, describe the available compensation to subjects in the event that such injury should occur.**

Response:

23.2 Provide a copy of contract language, if any, relevant to compensation for research related injury.

NOTE: If the contract is not yet approved at the time of this submission, submit the current version here. If the contract is later approved with **different language regarding research related injury**, you must modify your response here and submit an amendment to the IRB for review and approval.

Response:

24.0 Economic Burden to Subjects

24.1 Describe any costs that subjects may be responsible for because of participation in the research.

NOTE: Some examples include transportation or parking.

Response:

There is no cost for subjects to participate in this study.

- N/A: This study is not enrolling subjects, or is limited to records review procedures only. This section does not apply.

25.0 Compensation for Participation

25.1 Describe the amount and timing of any compensation to subjects, including monetary, course credit, or gift card compensation.

Response:

- N/A:** This study is not enrolling subjects, or is limited to records review procedures only. This section does not apply.
- N/A:** There is no compensation for participation. This section does not apply.

26.0 Consent Process

26.1 *Indicate whether you will be obtaining consent.*

NOTE: This does not refer to consent documentation, but rather whether you will be obtaining permission from subjects to participate in a research study. Consent documentation is addressed in Section 27.0.

- Yes** *(If yes, Provide responses to each question in this Section)*
- No** *(If no, Skip to Section 27.0)*

26.2 *Describe where the consent process will take place. Include steps to maximize subjects' privacy.*

Response:

The consent process will take place in the patient's private room in the ED. We will find the best time to approach the patients and their legal guardians for consenting purpose to avoid the interruption of patient's care as well as to protect patient's privacy. No other people will be in the patient's room beside the patient and the legal guardian when we obtain the consent.

26.3 *Describe how you will ensure that subjects are provided with a sufficient period of time to consider taking part in the research study.*

NOTE: It is always a requirement that a prospective subject is given sufficient time to have their questions answered and consider their participation. See "SOP: Informed Consent Process for Research (HRP-090)" Sections 5.5 and 5.6.

Response:

Enough time will be given to the legal guardian/participant to review the informed consent and to allow them understand the study completely, so they can make a clear informed decision. All questions will be addressed before obtaining the signatures from the legal guardian/participant.

26.4 *Describe any process to ensure ongoing consent, defined as a subject's willingness to continue participation for the duration of the research study.*

Response:

This study does not involve follow-up procedure. The legal guardian and participant will be informed that they have right to withdraw from the study at any time before the consent is being signed. The PI's contact information is listed in the informed consent.

26.5 Indicate whether you will be following “SOP: Informed Consent Process for Research (HRP-090).” If not, or if there are any exceptions or additional details to what is covered in the SOP, describe:

- The role of the individuals listed in the application who are involved in the consent process
- The time that will be devoted to the consent discussion
- Steps that will be taken to minimize the possibility of coercion or undue influence
- Steps that will be taken to ensure the subjects’ understanding

Response:

We have reviewed and will be following “SOP: Informed Consent Process for Research (HRP-090).”

Non-English Speaking Subjects

N/A: This study will not enroll Non-English speaking subjects.
(Skip to Section 26.8)

26.6 Indicate which language(s) other than English are likely to be spoken/understood by your prospective study population or their legally authorized representatives.

NOTE: The response to this Section should correspond with your response to Section 6.4 of this protocol.

Response:

26.7 If subjects who do not speak English will be enrolled, describe the process to ensure that the oral and written information provided to those subjects will be in that language. Indicate the language that will be used by those obtaining consent.

NOTE: Guidance is provided on “SOP: Informed Consent Process for Research (HRP-090).”

Response:

Cognitively Impaired Adults

N/A: This study will not enroll cognitively impaired adults.
(Skip to Section 26.9)

26.8 Describe the process to determine whether an individual is capable of consent.

Response:

Adults Unable to Consent

N/A: This study will not enroll adults unable to consent.
(Skip to Section 26.13)

When a person is not capable of consent due to cognitive impairment, a legally authorized representative should be used to provide consent (Sections 26.9 and 26.10) and, where possible, assent of the individual should also be solicited (Sections 26.11 and 26.12).

26.9 *Describe how you will identify a Legally Authorized Representative (LAR). Indicate that you have reviewed the “SOP: Legally Authorized Representatives, Children, and Guardians (HRP-013)” for research in New York State.*

NOTE: Examples of acceptable response includes: verifying the electronic medical record to determine if an LAR is recorded.

Response:

We have reviewed and will be following “SOP: Legally Authorized Representatives, Children, and Guardians (HRP-013).”

26.10 *For research conducted outside of New York State, provide information that describes which individuals are authorized under applicable law to consent on behalf of a prospective subject to their participation in the research. One method of obtaining this information is to have a legal counsel or authority review your protocol along with the definition of “legally authorized representative” in “SOP: Legally Authorized Representatives, Children, and Guardians (HRP-013).”*

Response:

This study will not be performed outside of NYS.

26.11 *Describe the process for assent of the adults:*

- *Indicate whether assent will be obtained from all, some, or none of the subjects. If some, indicate which adults will be required to assent and which will not.*

Response:

- *If assent will not be obtained from some or all subjects, provide an explanation of why not.*

Response:

26.12 *Describe whether assent of the adult subjects will be documented and the process to document assent.*

NOTE: The IRB allows the person obtaining assent to document assent on the consent document using the “Template Consent Document (HRP-502)” Signature Block for Assent of Adults who are Legally Unable to Consent.

Response:

Subjects who are not yet Adults (Infants, Children, and Teenagers)

N/A: This study will not enroll subjects who are not yet adults.
(Skip to Section 27.0)

26.13 *Describe the criteria that will be used to determine whether a prospective subject has not attained the legal age for consent to treatments or procedures involved in*

the research under the applicable law of the jurisdiction in which the research will be conducted (e.g., individuals under the age of 18 years). For research conducted in NYS, review “SOP: Legally Authorized Representatives, Children, and Guardians (HRP-013)” to be aware of which individuals in the state meet the definition of “children.”

NOTE: Examples of acceptable responses include: verification via electronic medical record, driver’s license or state-issued ID, screening questionnaire.

Response:

This study is conducted in NYS; we will use the SOP HRP-013 as the criteria to determine if a subject is not yet an adult. We will check patient’s birthdays in the electronic medical chart.

26.14 *For research conducted outside of New York State, provide information that describes which persons have not attained the legal age for consent to treatments or procedures involved the research, under the applicable law of the jurisdiction in which research will be conducted. One method of obtaining this information is to have a legal counsel or authority review your protocol along the definition of “children” in “SOP: Legally Authorized Representatives, Children, and Guardians (HRP-013).”*

Response:

This study will be conducted only in NYS.

26.15 *Describe whether parental permission will be obtained from:*

Response:

- One parent even if the other parent is alive, known, competent, reasonably available, and shares legal responsibility for the care and custody of the child.
- Both parents unless one parent is deceased, unknown, incompetent, or not reasonably available, or when only one parent has legal responsibility for the care and custody of the child.
- Parent permission will not be obtained. A waiver of parent permission is being requested.

NOTE: The requirement for parent permission is a protocol-specific determination made by the IRB based on the risk level of the research. For guidance, review the “CHECKLIST: Children (HRP-416).”

26.16 *Describe whether permission will be obtained from individuals **other than parents**, and if so, who will be allowed to provide permission. Describe your procedure for determining an individual’s authority to consent to the child’s general medical care.*

Response:

Parental permission will be obtained from the subject’s legal guardian who could be an individual other than the parents. These individuals need to show the legal document to

our ED registration staff for their authorities to consent the children for medical care. We will approach the patient and his/her legal guardian for study consenting purpose after the patient is being registered.

26.17 Indicate whether assent will be obtained from all, some, or none of the children. If assent will be obtained from some children, indicate which children will be required to assent.

Response:

Assent will be obtained from all children who are between 7-17 years of age.

26.18 When assent of children is obtained, describe how it will be documented.

Response:

Children will sign their names on the assent document.

